#### **4.3.e Research Aim 3 Question: Characteristics of Sustainable Testing Sites and Sustained use of Effective Approaches**

Qualitative thematic analyses will be used to code and segregate data derived from key stakeholder interviews and meeting notes from quarterly reports to categorize, synthesize, and interpret information. Responses will be categorized and coded for engagement themes (acceptability, penetration, adoption, fidelity) following a multi-step qualitative analysis process. We will independently conduct first-level coding to establish broad engagement themes. Next, we will independently conduct the second level of coding, meeting several times throughout the process to discuss areas of disagreement until consensus is reached. At the conclusion of coding we will have established ratings for level achieved for each engagement theme. Next, to the extent there is sufficient variability in the engagement ratings, we will examine correlations between engagement ratings and the number of sites within a community that have sustained testing (e.g., 80% or greater capacity) and use of efficacious interventions (e.g., number of times data-based decisions made). We acknowledge power to detect significant meaningful correlations is low given this is a community-based research question.

Thus, within each community, we will also rank order sites by outcomes and examine mean engagement rating scores which will provide additional evidence as to which engagement factors are associated with successful sustainability.

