The overall goal of our proposed research is to implement a culturally-tailored community outreach and testing program to increase the reach, access, uptake, and impact of testing in Latinx communities in Oregon. This project will fully integrate with the NIH Rapid Acceleration of Diagnostics (RADx) consortium and its Coordination and Data Collection Center (CDCC). With guidance and leadership from our Latinx Community and Scientific Advisory Board, we will launch the proposed testing program which will result in 36 community testing sites to serve Latinx communities. For the proposed research activities, we will test the following questions:

- 1) Do culturally-informed interventions ('Promotores') increase test rates and health behaviors?
 - a. Community-level intervention to increase participation in testing: Evaluate whether 'Promotores de Salud,' a culturally-tailored outreach intervention that includes psychoeducation, information support, and motivational strategies to address barriers, results in more tests completed and more sites testing at full capacity, as compared to basic community-level outreach services.
 - b. Individual-level booster intervention to change future health behavior: Examine whether a brief, individual-level 'Promotores de Salud' intervention held during a testing event (compared to distribution of a pamphlet only) results in greater use of strategies that reduce transmission at the community and individual level. Individual moderators (e.g., substance use, perceived threat, health literacy, social determinants) will also be examined. We further hypothesize that this intervention will increase future test rates through repeat testing visits and

through ‘snowball’ recruitment of friends and family to attend future testing events.

C. Methods, Materials and Analysis

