Within the SMART, a measure of initial response is assessed following implementation of the primary outreach approaches in order to evaluate each site's need for further adaptation. In this way, testing is tailored to meet the needs of communities and their Latinx individuals and families by providing enhanced testing strategies to slow-responding sites. This measure of initial response is referred to as a primary tailoring variable. In the proposed study, the primary tailoring variable is whether a site is operating at a threshold of 80% testing capacity, based on the frequency and per capita testing rates and presumption of 50 tests per testing event. The AIS each represent distinct plans of testing outreach approaches. Within the SMART, it is then possible to evaluate which adaptive sequence is the most effective in impacting Latinx testing rates and secondary outcomes such as health maintenance behaviors.

Specifically, the proposed RADx SMART includes 4 embedded adaptive intervention strategies (AIS). Sites and individuals in the proposed Latinx sampling frame will receive one of two first-stage implementation outreach strategies: Basic Outreach approaches or Basic Outreach plus Promotoras Comunitarias. Primary outcomes will be site level testing rates and individual level COVID-19-related health behaviors. After the initial 4 weeks (2 testing events), sites will be re-randomized in the second-stage randomization to either stay the course stationary events or to a mobilization intervention. Thus, for the primary criterion outcome of testing capacity, the SMART design includes 4 embedded site level adaptive intervention strategies (AIS): (1) starting with culturally adapted Basic Outreach, and staying the course; (2) starting with Basic Outreach followed by mobilization intervention; (3) starting with Basic Outreach plus Promotoras Comunitarias and staying the course; and (4) starting with Basic Outreach plus Promotoras Comunitarias plus mobilization intervention. In addition, as a booster to the Promotoras Comunitarias intervention, for health behavior outcomes, individuals tested at Basic Outreach sites will receive pamphlet health promotion pamphlets, and those tested at Promotoras Comunitarias sites, will receive a health pamphlet plus a Promotoras de Salud intervention.

[figure not shown]

Figure 4.3.1

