#### **4.3.c Recruitment of 36 Communities in 6 Counties into the Testing Program**

This testing program will build on existing partnerships with 6 county public health authorities in Oregon (see letters of support), that are either designated as a rural county by the Office of Management and Budget (Lincoln, Douglas, Josephine) or have a significant rural population (Lane, Marion, Benton). We will establish contracts with each county to provide them with staffing resources to support additional testing in Latinx communities. In addition, we will work with each county public health agency to develop a County Collaborative that includes key community stakeholders in the Latinx community, including those representing Latinx serving organizations such as non-profits and churches. The focus of the County Collaboratives is to engage the implementation process described in the implementation strategy. Leveraging the county collaboratives' knowledge of county communities, 6 communities (identified by zip code or zip code cluster) within each county will be selected for site implementation. Given that proximity is a critical component for reducing barriers to access in rural communities, and given the composition of the 6 counties, most of the 36 communities who participate in the testing program will be rural. We will employ *a priori* stratification by county and rurality to balance potential confounders, to reflect the hierarchical structure of the design in the analytic plan. Specifically, for the first randomization, within each county, 3 communities will be randomized to the treatment condition and 3 to the control condition (total of 18 per condition, 36 total).

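### Aim 3 correlates engagement with a count of sites above an 80% capacity line, although percentage of capacity is continuous and already computable; the cut loses power, by an amount the SAP does not let one fix

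*SAP*

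**What the plan says.** SAP section 4.3.e codes stakeholder interviews and meeting notes into engagement ratings. It then plans the following: "to the extent there is sufficient variability in the engagement ratings, we will examine correlations". Two correlates are named. The first is the "number of sites within a community that have sustained testing (e.g., 80% or greater capacity"). The second is "use of efficacious interventions (e.g., number of times data-based decisions made"). The section adds that "within each community, we will also rank order sites by outcomes and examine mean engagement rating scores". On power it says only this: "We acknowledge power to detect significant meaningful correlations is low given this is a community-based research question". It gives no number of units, expected correlation, alpha or power for Aim 3.

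The 80% figure also appears in SAP section 4.3.a, as the tailoring variable for initial response: "whether a site is operating at a threshold of 80% testing capacity, based on the frequency and per capita testing rates and presumption of 50". The 50 is the presumed number of tests at each event. What lies beneath the line is therefore a graded quantity. Protocol section C, data point 1, gives the researchers test-level records with site zip code and testing date, plus a list of site addresses and dates. Tests per site and event can be derived from these without new data collection.

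The unit is not settled. SAP section 4.3.c has "6 communities (identified by zip code or zip code cluster) within each county will be selected for site implementation" in 6 counties, which makes 36 communities. Protocol section B describes a program "which will result in 36 community testing sites to serve Latinx communities". That is one site per community. Section 4.3.e nevertheless speaks of counting and ranking several sites within a community.

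**The concern.** Each site is reduced to above or below the line before anything is summed or correlated. A site at 79% of capacity counts the same as one at 10%, and a site at 81% the same as one at 100%. The correlation being sought is weakened, and the result depends on how many sites happen to lie near 80%.

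The SAP attributes its low power to the community-level nature of the question. The cut adds a further loss that can be avoided. The correlations in 4.3.e are the SAP's main quantitative look at which engagement features go with sustained testing, so a real association would be somewhat more likely to be missed.

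**Working it through.** There is no Aim 3 power figure in the SAP to reproduce, so the check asks how much the cut costs under stated assumptions.

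**Inputs from the documents.** 36 sites and 36 communities, or 6 counties with 6 sites each (SAP 4.3.c; Protocol section B). Two-sided alpha .05 and response splits of 50/50, 80/20 and 20/80 (SAP 4.3.f). The alpha is stated there for comparing the adaptive strategies and the splits for initial response; using them for Aim 3 is an assumption.

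**Assumed.** The true correlation r, varied from .10 to .50 (county case: .40 to .60); bivariate normality; and, in the simulation for 36 units, an engagement rating with 4 levels.

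**Step 1: attenuation.** Cutting a normal outcome so that a share p lies above the line multiplies r by φ(z_p)/√(p(1−p)). This is 0.798 at p = .50 and 0.700 at p = .20 or .80.

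**Step 2: power with 36 one-site communities.** By Fisher's z, power ≈ Φ(atanh(r)·√(n−3) − 1.96), plus a negligible opposite tail except at small r. At r = .40 and n = 36:
- Uncut: atanh(.40)·√33 = 2.43, so power is Φ(0.47) = .68.
- 50/50 cut: r becomes .40 × 0.798 = .319, and power is .48.
- 80/20 cut: r becomes .40 × 0.700 = .280, and power is .38.

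| True r | Uncut, % | 50/50 cut, % | 80/20 cut, % | Loss by formula, points | Loss by simulation with 4-level rating, points |
|---|---|---|---|---|---|
| .10 | 8.9 | 7.5 | 6.9 | 1 to 2 | 1 to 2 |
| .20 | 21.4 | 15.2 | 12.8 | 6 to 9 | 5 to 8 |
| .30 | 42.8 | 28.9 | 23.2 | 14 to 20 | 12 to 18 |
| .40 | 68.2 | 47.6 | 37.9 | 21 to 30 | 18 to 29 |
| .50 | 88.4 | 68.0 | 55.5 | 20 to 33 | 20 to 34 |

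In the simulation at r = .40, power is .63 on the full scale, .60 on ranks, .44 with the 50/50 cut and .34 with the 80/20 cut. Moving to ranks therefore costs about 3 points, against 19 or 29 for the cut.

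**Step 3: six counties, a count of 0 to 6 sites each.** Here the correlation must be defined. If it is between the rating and the underlying county level, at .40 to .60, the loss is about 1 to 6 points. If .60 is the correlation with the observed county mean (intraclass correlation .2 to .4), power is about .25 uncut against .19 to .21 (50/50) or .16 to .17 (80/20), a loss of 4 to 9 points.

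**Step 4: what limits Aim 3 most.** The true r needed for 80% power is tanh((1.96 + 0.84)/√(n−3)). This is about .45 with 36 units and about .92 with 6. With six units, the number of units constrains the analysis far more than the cut does.

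**The case against.** The strongest reply is that 4.3.e already allows for most of this. The 80% line is only an example, the second correlate is an uncut count, sites are also ranked by outcomes, low power is conceded, and Aim 3 is largely qualitative with no declared test. Sustained testing is moreover a status, and 80% is the program's own operating threshold, so reusing it is coherent.

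Part of this stands. The status is of interest and its count should still be reported. The lack of an outside guideline for 80% is no defect in an implementation measure. Aim 3 is exploratory, so power is only a rough yardstick.

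The rest does not remove the point. Any other threshold also discards information. The count of data-based decisions measures something different. The ranking is within communities, so it does not restore the comparison between them, and with one site per community there is nothing to rank.

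Two stronger readings are tempting, and the documents support neither:
- **A fixed loss of about 12 to 33 points.** A reader might infer this as a property of the plan. It requires 36 one-site communities, a true correlation of about .30 to .50, and splits the SAP gives for initial response. The largest losses arise where uncut power is already about .6 or more, which fits poorly with an analysis described as low-powered. The one-site case also fits poorly with the section's talk of several sites per community.
- **A similar loss with counties.** A reader might calculate power of .75 against .57 or .42 for six counties at a correlation of .60. That takes .60 as a site-level correlation with independent site residuals. The correlation with county means is then .60/√(.36 + .64/6) = .88, which is not comparable with the .30 to .50 used for 36 units.

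**Conclusion.** The point holds as a low-cost improvement. Section 4.3.e cuts a continuous measure before correlating it and so gives up information that the trial already has. The attenuation, to about 0.80 or 0.70 of the site-level correlation, rests on normality and the assumed splits. The power loss rests further on the unit and the true correlation, neither of which the SAP states. It runs from 1 or 2 points to about a third of full power in percentage points with 36 one-site communities, and is small with six counties at moderate correlations. The documents do not show that the cut is the main reason for Aim 3's low power, or that removing it would make Aim 3 adequately powered. The undefined unit matters at least as much and should be settled in the same edit.

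**What to change.** In SAP section 4.3.e:

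- Make the main sustained-testing correlate the continuous percentage of capacity: tests completed divided by (50 × events held), averaged over a community's sites if it has more than one.
- Use Spearman correlations with confidence intervals across all communities.
- State whether the unit is the 36 communities or the 6 counties.
- Keep the number or share of sites at 80% or more as a descriptive summary of sustained status.

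The cost is a sentence or two of SAP wording, with no new data, staff or participants. There are two downsides. The result is expressed on the capacity scale and not as sustained or not. A mean over several sites can also mask one failing site, which the retained count would show.

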#### 4.3.f Power

Power for detecting the optimal AIS was estimated using the SMARTAR package 1.0.0 in R R^71. We chose a power convention of .80 with a two-sided alpha level of .05 to reduce the probability of obtaining a false positive (Type-I error). For research question 1, balanced response rates of 50% of sites having adequate response and 50% slow responding, 36 sites for a continuous outcome (e.g., rates) can minimally detect a small difference of .27 among the combined group comparisons [(A+B+C+D) vs (E+F+G+H)], and power to minimally detect a medium effect of .54 (n=18 sites) [(D+H) vs (C+G)]. For the global test of the optimal treatment strategy (n=36 sites), the study is powered to minimally detect an effect of .40, a moderate effect. Power for detecting the optimal AIS was estimated using the SMARTAR package 1.0.0 in R^71.

We must also consider response scenarios that include either more slow-responding or even less slow responding sites before the tailoring intervention (i.e., 80% of the randomly allocated sites responded at capacity and 20% were below threshold; or alternatively, only 20% responded and 80% were below capacity initially). In each of these "unbalanced" response scenarios, power for research question 1 is the same as the balanced design above. Although we do not anticipate such a large range of slow responding sites based on our preliminary testing; for the slow-responding sites only, a bracket range of 80/20 response ratio (resulting in 8 slow responding sites [(D+H) vs (C+G)]) to a high of 20/80 ratio (resulting in 28 slow responding sites [(D+H) vs (C+G)]). In these scenarios, for research question 2, the study is powered .80 to minimally detect a difference of 1.3 (a large effect) or to minimally detect a moderate effect of .35 (a moderate effect), respectively, for 8 to 28 total slow responding sites for research question 2.

[figure not shown]

Figure 4.3.f Power Curve.

Finally, when considering power for individual level data, a mixed model with two levels (individuals nested within sites) we must consider full capacity scenarios where implementation is realized at full capacity (roughly 3600 tests) to scenarios that obtain a smaller number of individual tests based on response patterns by site. In this case, that is the balanced scenario shown in Figure 4.3.1 given half of the sites are slow responding. That scenario projects a maximum of 2520 level-1 testing units sampled from 36 sites and achieves .80 power to detect a difference of .22 (a small effect) among the group conditions for randomization 1 conditions A1, randomization 2 conditions A2, and their crossed A1A2 interaction, and an intraclass correlation of .05 for the test of comparative intervention strategies from the primary equation shown above. Thus, the study is adequately powered for all multilevel data scenarios for minimum response to maximum response to detect small effect sizes. Power for individual comparisons among the 4 embedded AISs is shown in Figure 4.3.f.

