#### 4.3.b Embedded AIS Research Questions and Aims

The specific research questions and aims are the following. Question 1a: Is Basic Outreach plus Promotoras Comunitarias more effective for maximizing testing capacity than Basic Outreach? Question 1b: For individuals tested, is Pamphlet plus Promotoras de Salud more effective than Pamphlet only in supporting positive health behaviors for individuals tested? [(A+B+C+D) vs (E+F+G+H)]. Research Aim Question 2: Among slow responding sites, does the mobilization intervention yield an increase in individual positive health behaviors and in site testing capacity? [(D+H) vs (C+G)].

Each of these AIS research questions is depicted in Figures 4.3.2 through 4.3.3:

**Question 1a:** Is Basic Outreach plus Promotoras Comunitarias more effective for testing capacity than Basic Outreach alone, for Latinx communities?

**Question 1b:** For individuals tested, is Pamphlet plus Promotoras de Salud more effective than Pamphlet only in supporting positive health behaviors for individuals tested, and increasing site testing rates?

**Aim 1a:** Is Basic Outreach plus Promotoras Comunitarias more effective for testing capacity than Basic Outreach alone?

**Aim 1b:** For individuals tested, is Pamphlet plus Promotoras de Salud more effective than Pamphlet only in supporting positive health behaviors for individuals tested, and increasing testing rates?

[figure not shown]

Figure 4.3.2

**Research Aim Question 2:** Among slow responding sites, does the mobilization intervention yield an increase in site testing capacity?

**Aim 2:** Among slow responding sites, does the mobilization intervention yield increase in site testing capacity?

[figure not shown]

Figure 4.3.3

In addition to research questions 1 and 2, the SMART design also allows for an omnibus comparison; after starting with Basic Outreach or Basic Outreach + Promotoras Comunitarias, we can examine which of the embedded adaptive intervention strategies is more effective overall for testing capacity and health behavior maintenance [A vs B vs C vs D vs E vs F vs G vs H]. Although not a specific aim of the proposed study, agencies and stakeholders may be particularly interested in this question and our study design will allow us to test this, focusing on the combined R1 and R2 strategies.

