#### **4.3.d Data Analysis for Aims 1 and 2**

For the primary evaluation aims for determining the optimal strategy for testing Latinx communities and the four adaptive intervention strategies, we will employ standard normal theory generalized linear modeling analysis of covariance fractional factorial analyses using pre-post assessment scores for site and individual level outcomes. Research Question 1 will focus on the combined effects of A1 randomization groups [(A+B+C+D) vs (E+F+G+H)]. Research Question 2 will focus on which A2 strategy works best for slow-responding sites [(D+H) vs (C+G)]. To address the non-independence of subjects in the embedded adaptive intervention designs and crossed factors, we will estimate linear mixed models with weighted least squares using the design effects coding shown in Table 4.3.1.

The general equation to estimate the optimal strategy is given by

$$E[Y|A_1, A_2, O_1] = \beta_0 + \beta_1 A_1 + \beta_2 A_2 + \beta_3 A_1 A_2 + \gamma^T O_1$$

where  $E$  is the expected value of the outcome,  $A_1$  is the initial treatment randomization,  $A_2$  is the second stage treatment randomization and  $\gamma^T$  are the estimates for covariate  $O_1$ , the pre-test covariate. For binary and count data we will employ generalized linear modeling and logit, probit, and poisson link functions for criterion outcomes such as frequency of tests, re-tests, and discrete event behaviors.

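### SAP 4.3.f says 36 sites can detect a small difference of .27; the site-level comparison detects about 0.96 SD, or .83 to .58 SD with a pre-test correlation of .5 to .8

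*SAP*

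**What the plan says.** Section 4.3.f sets power at .80 and two-sided alpha at .05, and gives these site-level detectable effects:

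- First-stage comparison, all sites: "36 sites for a continuous outcome (e.g., rates) can minimally detect a small difference of .27 among the combined group comparisons".
- Second-stage comparison in slow-responding sites, half of sites slow: "power to minimally detect a medium effect of .54 (n=18 sites").
- The same comparison with 8 or 28 slow sites: "the study is powered .80 to minimally detect a difference of 1.3 (a large effect) or to minimally detect a moderate effect of .35", respectively.
- Global test, 36 sites: "the study is powered to minimally detect an effect of .40, a moderate effect".

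Allocation is in section 4.3.c: within each county "3 communities will be randomized to the treatment condition and 3 to the control condition (total of 18 per condition, 36 total"). That section also plans "stratification by county and rurality to balance potential confounders, to reflect the hierarchical structure of the design in the analytic plan". Section 4.3.d plans "analysis of covariance fractional factorial analyses using pre-post assessment scores for site and individual level outcomes", but no pre-post correlation is given. The text says the site-level figures come from the SMARTAR package and states neither the effect metric nor the degrees of freedom. Figures 4.3.1 and 4.3.f and Table 4.3.1 could not be seen in the copy reviewed.

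**The concern.** The words difference, small, medium and large read as standardized mean differences, yet two arms of 18 units cannot normally detect a difference of about a quarter of an SD. The figures also behave oddly among themselves: halving the number of sites exactly doubles the stated effect, whereas a mean difference would grow by roughly the square root of two.

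Site-level testing rate is a primary outcome, and this is its primary comparison. If the power statement stands, a null result for Promotores outreach could be read as evidence against even a small effect, when the trial had little chance of finding one.

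**Working it through.** **Inputs.** Power .80, two-sided .05, and effects of .27, .54, .35 and 1.3 for 36, 18, 28 and 8 sites (4.3.f); 18 versus 18 sites (4.3.c); one pre-test covariate (4.3.d). Assumption: a 1:1 split of the slow sites, which the text does not give.

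**Step 1: can the stated figures be reproduced?** No 1-df two-group calculation gives .80 power at .27. The closest match is a noncentrality per site. A 2-df chi-square test needs noncentrality 9.635 for .80 power, and 9.635/N gives .268, .535, .344 and 1.204 for N = 36, 18, 28 and 8. A 7-df test gives 14.351/36 = .399. These match .27, .54, about .35 and the global .40; the 8-site value (1.3) fits less well. The text states neither this metric nor these degrees of freedom.

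**Step 2: a scaling check that needs no SD or correlation.** For a mean difference with one common SD and one common correlation, both cancel when each figure is divided by the 36-site figure.

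| Sites | Stated | Stated / .27 | Expected ratio, 0 or 1 covariate | N × stated |
|---|---|---|---|---|
| 36 | .27 | 1 | 1 | 9.72 |
| 18 | .54 | 2.00 | 1.46–1.47 | 9.72 |
| 28 | .35 | 1.30 | 1.14–1.15 | 9.80 |
| 8 | 1.3 | 4.81 | 2.48–2.58 | 10.40 |

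The four figures cannot all be mean differences, raw or standardized, under one set of assumptions. The last column shows that they scale nearly as 1/N, as a squared index would.

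**Step 3: reading 1, a standardized site-level difference d.** The noncentrality of the t statistic is δ = d√N / (2√(1 − r²)), with N − 2 degrees of freedom unadjusted and N − 3 with one covariate.

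- At d = .27, N = 36, r = 0: δ = .27 × 6/2 = .81, and power is 12%.
- For .80 power on 34 df, δ must be 2.884, so d = 2 × 2.884/6 = 0.96.
- With the covariate (33 df), d = .962√(1 − r²). At r = .5 this is .962 × .866 = .83; at r = .8, .962 × .6 = .58. It reaches .50 only at r = .85.
- To reach .27: r = √(1 − (.27/.962)²) = .96.
- Power at .27 is 15%, 26% and 44% for r = .5, .8 and .9.

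| Sites | Stated | Power at stated value, unadjusted | Detectable SD, unadjusted | Detectable SD, r = .5 to .8 | r needed |
|---|---|---|---|---|---|
| 36 | .27 | 12% | 0.96 | .83 to .58 | .96 |
| 18 | .54 | 19% | 1.41 | 1.22 to .85 | .92 |
| 28 | .35 | 14% | 1.10 | .95 to .66 | .95 |
| 8 | 1.3 | 34% | 2.38 | 2.15 to 1.49 | .85 |

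County and rurality strata do not change this. With 0 to 11 degrees of freedom for strata, pre-test and strata together must explain about 92% of between-site variance for .27 to be detectable.

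**Step 4: reading 2, f-squared on a 1-df two-arm contrast.** With noncentrality f² × N, power at the four stated values is 86%, 83%, 85% and 77% (36, 18, 28 and 8 sites). Converting by d = 2√f²: 2√.27 = 1.04 SD, 2√.54 = 1.47 SD, 2√.35 = 1.18 SD and 2√1.3 = 2.28 SD. The first three are not small, medium and moderate differences.

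**Step 5: other metrics for .27.** As Cohen's f, d = 2 × .27 = .54; unadjusted power is 35% and r = .83 is needed. As d-squared, d = √.27 = .52; power is 33% and r = .84 is needed.

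**Step 6: global .40 with 36 sites.** Power is 45% as f or 86% as f-squared for four strategies, and 29% or 68% for the eight cells A to H.

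**Secondary check: individual-level outcomes.** Section 4.3.f gives a detectable .22 for 2520 people in 36 sites at an ICC of .05, then concludes that power is adequate for small effects in every multilevel scenario. Assuming 2520/36 = 70 people per site, the design effect is 1 + 69 × .05 = 4.45. The unadjusted detectable effect is 2 × 2.80 × √(4.45/2520) = .235 (normal) or .242 (t). A covariate R² of 1 − (.22/.235)² = 13% to 1 − (.22/.242)² = 18% closes that gap.

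For slow sites only, unlimited people per site gives the unadjusted floor 2k√(.05/J), with J sites and k the normal or t multiplier for .80 power: .44–.53 for 8 sites, .30–.31 for 18 and .24–.25 for 28. All exceed .22. Section 4.3.b first words Question 2 as "Among slow responding sites, does the mobilization intervention yield an increase in individual positive health behaviors and in site testing capacity", so the individual-level contrast is raised there.

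**The case against.** The strongest reply is that the scaling check itself rules out reading 1 for the set of figures, so the software output may be sound and the fault one of labelling. That is probably what happened, and it stands as an explanation. It does not rescue the sentence: on the squared scale .27 is about 1 SD, and the text still calls it a small difference. The conversion does assume a 1-df two-arm contrast, which reproduces three of the four values less closely than the 2-df noncentrality.

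Other defences go less far:

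- **Raw rate difference.** This gives .80 power if the site SD is .27/.961 = .28. No SD is stated, small could not be judged on that scale, and one common SD conflicts with step 2.
- **Repeated testing events.** Assuming 20 events per site (two per four weeks over 40 weeks) and standardizing on the event-level SD, the detectable effect is .30 unadjusted at an event ICC of .05, but .56 at .30. The documents give no such ICC, and 4.3.f counts sites.
- **Covariates other than the pre-test.** They could supply part of the required variance, so .96 is a total multiple correlation. About 92% explained variance is still required.
- **Unseen figures and table.** They may name the metric. That would settle which reading applies, but would not make the effect small.

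The secondary point is weaker. The formal Aim 2 names only site testing capacity, the .22 is said to cover the second-stage factor, and section 4.3.a does not clearly limit re-randomization to slow sites.

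**Conclusion.** The concern holds. With 36 sites split 18 and 18, the detectable site-level difference is 0.96 SD unadjusted and .83 to .58 SD for a pre-test correlation of .5 to .8. It falls below .50 SD only above r = .85 and reaches .27 only at about .96. If .27 is instead f-squared, power is about right but the effect is about 1.04 SD. Either way, the stated ability to detect a small effect is not a property of this design.

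The calculation rests on .80 power, two-sided .05, sites as the unit and exact noncentral t and F distributions; results for slow sites also assume a 1:1 split. Which metric the SAP intended is an inference from the 1/N scaling. That the size labels are wrong does not depend on that inference.

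**What to change.** Revise the text of 4.3.f:

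1. Name the effect metric, degrees of freedom, second-stage split and assumed pre-post correlation. If a figure or table already names them, repeat them in the text.
2. Give site-level detectable differences in SD units. Unadjusted with a 1:1 split, these are about 0.96 (36 sites), 1.41 (18), 1.10 (28) and 2.38 (8). Beside them give the planned ANCOVA over a stated range of r; for r = .5 to .8 the step 3 table supplies the values. Say whether county and rurality strata are in the model.
3. Correct the size labels to match.
4. Say whether the global .40 is f or f-squared, and whether it compares four strategies or eight cells.

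Items 2 and 3 are the essential ones; the rest let a reader reproduce them. As a secondary edit, limit the closing individual-level power statement to the 36-site contrasts or add detectable effects for slow sites, and state the covariate R² behind .22.

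The cost is SAP wording only. Design, sample size and analysis do not change, but the stated detectable effects become less favourable.
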